10.2 Power to Detect Effects in Primary Outcome

This is a feasibility pilot and therefore is not powered to detect significant differences relative to the baseline period. The use of a non-powered pilot design is called for by the MP3 mechanism. A sample of 200 individuals per intervention city was selected based on what was determined to be achievable given budget and time constraints. It is also anticipated that this number will provide estimates of key parameters with sufficient precision. For instance, the prevalence of our binary benchmarks (home HIV

test orders, PrEP initiation) would be estimable with the following 95% confidence intervals half-width at specified prevalences: $20\% \pm 4\%$; $30\% \pm 5\%$; $50\% \pm 5\%$.

Led by the study statistician, additional analyses will be conducted to assess (1) preliminary efficacy with endpoints measuring change from baseline to intervention periods in HIV testing, condom use, and PrEP use, (2) theoretical efficacy with endpoints in the PrEP cascade and UTAUT2 constructs, and (3) process outcomes with endpoints of new HIV testers, new condom users, and app use metrics. These assessment will leverage the pilot's interrupted time series design and inform future clinical trial design.

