Study Design:

The pilot study will be an interrupted time series cohort of 400 MSM. In two cities, a three-month baseline standard of care (SOC) period with measurement at 0 and 3 months will be followed by a 12-month intervention period with the measurement at 6, 9, 12, and 15 months. The longitudinal design will allow for 1) assessment of feasibility and acceptability outcomes, 2) development of the logistical and operational needs to provide the app-based intervention, and 3) development of estimates for key parameters to design a future, definitive study to determine intervention efficacy.

Standard of care will consist of the existing Blued app and local health services. Blued app access currently includes health education components such as information regarding HIV testing and pre-recorded health messages from Chinese celebrities. Participants will have access to in-person no-cost services for HIV testing and condom pick-up from local non-governmental organizations (NGOs) that support MSM in both cities.

At three months, participants will be provided with educational materials in the health portal as well as theory-based HIV prevention messages, along with home HIV test kits and condoms. This intervention will have a health portal that houses all HIV prevention functionalities. The exact nature of the interventions included will be further defined by the qualitative work, as additional services may be identified as essential to an HIV prevention package in China. These may include services such as peer support or stigma reduction. Additionally, participants will receive PrEP medication, laboratory, and care costs free of charge.

In the portal, users will be able to explore health-supporting functions of the app and access offline services, including behavioral risk assessments, an HIV prevention platform, HIV testing, linkage to care for those testing positive for HIV, in-app screening and referral to HIV pre-exposure prophylaxis (PrEP) and sexually transmitted infection (STI) services, and provision of PrEP with emtricitabine/tenofovir disoproxil fumarate (FTC/TDF).

Study Population:

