A total of 400 participants will be enrolled in the intervention with quarterly follow-up with a total of six surveys for each participant comprising enrollment/baseline (two surveys) and pilot intervention (four surveys). The survey will be team translated to ensure accuracy of the text and participant understanding.

Below is a diagram of the pilot study design:

[figure not shown]

Figure 1 Pilot Study Design Overview

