10.3 Preliminary Efficacy Assessment

Preliminary efficacy assessments will describe differences in outcomes for the intervention, compared to the baseline period, for the median number of HIV tests and the proportion reporting all anal sex acts as condom-protected. A generalized estimating equations (GEE) repeated measures analysis will be conducted for the binary outcome of HIV testing (test/not testing). The GEE model will contain the seven time periods with primary comparisons of 0-month (first baseline) measurement to 6-month (end wash-out baseline period measurement and to 12-month (end first intervention period) measurement. Time will be considered as a fixed effect to compare proportion tested across intervals, with a random intercept for individuals. A similar GEE model will be conducted for the condom outcome (always/not always condom use). Logistic regression models will be fitted to understand PrEP cascade progressions, with the main analysis being any forward progress (yes/no) in the overall cascade between 0-month and 15-month measurements. These analyses will consider variables of progression in the PrEP cascade. Time at which cascade progress was made (e.g. 3 months) will be entered as a co-variate. A multifaceted approach to address missingness for our outcomes will be used. Primary analyses will treat values as missing at random. Sensitivity analyses will re-analyze data using both last-value-carried-forward and multiple imputation methods.

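### The preliminary efficacy contrasts carry any background drift in full, although the plan says they draw on an interrupted time series

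*Combined protocol and SAP*

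**What the plan says.** The Schema and section 3.0 both call the pilot an interrupted time series. The Schema sets out "a three-month baseline standard of care (SOC) period with measurement at 0 and 3 months", then a "12-month intervention period with the measurement at 6, 9, 12, and 15 months". Section 3.0 gives the same count: "six surveys for each participant comprising enrollment/baseline (two surveys) and pilot intervention (four surveys". All 400 men receive the intervention (section 3.2), and no concurrent comparison group is described.

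Section 10.2 lists the additional analyses, beginning with preliminary efficacy, and says they will draw on the pilot's "interrupted time series design and inform future clinical trial design".

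Section 10.3 gives the model for HIV testing, with a similar one for condom use: "The GEE model will contain the seven time periods with primary comparisons of 0-month (first baseline) measurement". That month-0 survey is compared with two later points, "6-month (end wash-out baseline period measurement and to 12-month (end first intervention period) measurement". On time, it says: "Time will be considered as a fixed effect to compare proportion tested across intervals". It names no slope before the intervention, no change in level or slope at month 3, and no other allowance for background trend.

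**The concern.** In an interrupted time series the pre-intervention course stands in for the missing control group. The analysis in section 10.3 does not use that course. It subtracts the first survey from a later one, so whatever would have happened without Blued+ is counted as part of the change.

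Drift is not far-fetched here. Section 4.1 requires behavioural eligibility for PrEP, and the PrEP indications in section 5.4.1 include inconsistent condom use. Always using condoms is an outcome. If the guidance applied at entry uses similar criteria, some men enter at a high point of risk and would move back towards their usual behaviour untreated. Such drift need not be linear.

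At stake is how the preliminary efficacy results are read, and what they lend to the design of the definitive study under Aim 4.

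**Working it through.** **The plan's own figures.** Section 10.2 gives 95% half-widths of 4, 5 and 5 points at prevalences of 20%, 30% and 50%. With n = 400, 1.96 × √(p(1−p)/400) gives 3.92, 4.49 and 4.90 points, which match when rounded up. They concern single proportions for the benchmarks and do not bear on trend.

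**Inputs from the documents.** Surveys at months 0, 3, 6, 9, 12 and 15; intervention from month 3; n = 400; planned contrasts 0 v 6 and 0 v 12.

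**Assumptions, not in the documents.** Proportion p = 0.30, equal correlation ρ = 0.4 between any two surveys of the same man, full retention, and linear drift of d = 1 to 3 points per quarter.

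**Drift in the planned contrasts, with no intervention effect.** Month 6 is two quarters after month 0, and month 12 is four.

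| d (points per quarter) | 0 v 6 (2d) | 0 v 12 (4d) |
|---|---|---|
| 1 | 2 | 4 |
| 2 | 4 | 8 |
| 3 | 6 | 12 |

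**Precision with and without a trend correction.** For survey weights c that sum to zero, SE = √(p(1−p)(1−ρ) × Σc² / n). Here √(0.30 × 0.70 × 0.6 / 400) = 0.01775, so the half-width is 1.96 × 1.775 × √Σc² = 3.479 × √Σc² points.

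The baseline slope per quarter is (month 3 − month 0). Projecting it forward from month 3 gives these contrasts:

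- Month 6: month 6 − 2 × month 3 + month 0, so Σc² = 1 + 4 + 1 = 6.
- Month 12: month 12 − 4 × month 3 + 3 × month 0, so Σc² = 1 + 16 + 9 = 26.

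A model with one common slope over all six surveys plus a step at the switch can be checked with survey index 0 to 5 and a step of 0,0,1,1,1,1. The residual sum of squares of the step, after fitting intercept and time, is 1.333 − 4²/17.5 = 0.419. The equivalent Σc² is 1/0.419 = 2.39.

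| Estimate | Σc² | Half-width, p = 0.30, ρ = 0.4 | Range, p 0.20–0.50, ρ 0.3–0.5 |
|---|---|---|---|
| Plain difference | 2 | 4.9 | 3.9–5.8 |
| Common slope plus step | 2.39 | 5.4 | 4.3–6.3 |
| Drift-corrected, month 6 | 6 | 8.5 | 6.8–10.0 |
| Drift-corrected, month 12 | 26 | 17.7 | 14.1–20.9 |

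The month 0 to 3 change is itself a plain difference, so the drift per quarter is known to about ±4.9 points, and two points leave nothing with which to check linearity. Drift alone equals the plain half-width at 4.9/4 = 1.2 points per quarter for 0 v 12, and at 4.9/2 = 2.5 for 0 v 6. If only 320 men were retained (an assumption), every half-width would grow by √(400/320) = 1.12.

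**The labels.** Section 10.3 has seven periods against six surveys, and calls month 6 the end of a baseline wash-out although the Schema places it three months into the intervention. If the label is right and the month wrong, the first contrast becomes a check of drift within baseline. The month-12 contrast would still be unadjusted.

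**The case against.** The strongest reply is that the plan promises little. Section 10.1 makes feasibility and acceptability primary, section 10.2 says the pilot is not powered for change from baseline, and section 10.3 sets out to describe differences. All of that stands, and it limits the weight of the point. It does not remove it: lack of power concerns precision and does not warn of bias.

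Three stronger readings are tempting and are not supported:

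- A reader might infer that the plan claims to control background trend. No section says so. That property is inferred from the design label.
- A reader might infer that two baseline surveys cannot yield a trend at all. They can, because 400 men are measured at each. Time compared across intervals also lets the month 0 to 3 change be read from the planned model. What is missing is a pre-specified use of it. The common-slope model costs little precision, but it assumes linear drift and an effect that does not grow, and it takes much of its slope from intervention surveys.
- A reader might infer that the before-after difference will be the effect size for the definitive study. The Schema speaks of key parameters and section 10.2 of informing design. The only specific sample-size use is of structural equation coefficients (section 10.4).

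The label conflict in section 10.3 could also mean that a drift check was intended. That is possible, but the text does not settle it, and a check on the first contrast would not adjust the second.

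**Conclusion.** The point holds in limited form. As written, both planned contrasts contain all of any background drift: 2 to 6 points at month 6 and 4 to 12 at month 12, for an assumed 1 to 3 points per quarter. The existing surveys support a weak but usable correction at month 6 (about ±8.5 points). At month 12 (about ±17.7) it is too imprecise to tell drift from effect. The half-widths rest on the assumed proportion, correlation and full retention, and the correction also rests on linear drift that the data cannot test. The size of any actual drift is unknown. Only the secondary, unpowered preliminary efficacy analysis is affected. The change is worth making because it is cheap and governs how those results may be described.

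**What to change.** In section 10.3:

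- Reconcile the number of periods and the month labels with the six-survey schedule.
- Report the month 0 to 3 change with its 95% confidence interval beside every before-after contrast, as the internal estimate of background drift.
- Add month 6 minus twice month 3 plus month 0 as a sensitivity contrast.
- State that later changes cannot be separated from trend.

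In the Schema and sections 3.0 and 10.2, describe the efficacy results as uncontrolled before-after differences in a single-group cohort with two pre-intervention surveys. If any such difference informs Aim 4, carry it forward with that caveat.

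The cost is wording and one extra contrast from data already planned. The downside is a weaker stated claim and, for the sensitivity contrast, an interval about √(6/2) = 1.7 times as wide.

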10.3 Preliminary Efficacy Assessment

Preliminary efficacy assessments will describe differences in outcomes for the intervention, compared to the baseline period, for the median number of HIV tests and the proportion reporting all anal sex acts as condom-protected. A generalized estimating equations (GEE) repeated measures analysis will be conducted for the binary outcome of HIV testing (test/not testing). The GEE model will contain the seven time periods with primary comparisons of 0-month (first baseline) measurement to 6-month (end wash-out baseline period measurement and to 12-month (end first intervention period) measurement. Time will be considered as a fixed effect to compare proportion tested across intervals, with a random intercept for individuals. A similar GEE model will be conducted for the condom outcome (always/not always condom use). Logistic regression models will be fitted to understand PrEP cascade progressions, with the main analysis being any forward progress (yes/no) in the overall cascade between 0-month and 15-month measurements. These analyses will consider variables of progression in the PrEP cascade. Time at which cascade progress was made (e.g. 3 months) will be entered as a co-variate. A multifaceted approach to address missingness for our outcomes will be used. Primary analyses will treat values as missing at random. Sensitivity analyses will re-analyze data using both last-value-carried-forward and multiple imputation methods.

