Despite the substantial epidemic, the use of HIV prevention services among MSM is low. In the 61-city survey, over half of the sample reported inconsistent condom use with male partners in the prior year.⁴ In our four-city data, 46% (1584/3457) of sexually active MSM reported inconsistent condom use. Although sexually transmitted infection (STI) control is a priority in China's HIV prevention plan¹¹, less than a third of MSM in China have ever been tested for syphilis,¹² and our four-city survey found that only 30% had tested for any STI in the past year. In terms of HIV testing, a systematic review in 2014 documented an annual period prevalence of HIV testing of 38% among MSM in the most recent reporting period,¹³ and our four-city survey found 52% annual testing prevalence. Taken together, these data suggest the need for improved coverage of each step of the HIV prevention continuum, including the promotion of HIV testing, increased condom uptake, and screening for STIs.

Primary reasons for low levels of HIV testing include privacy concerns and nondisclosure of sexual identity; these problems are readily addressable through home-based services. Several studies have found privacy concerns are an important barrier to HIV testing among Chinese MSM,¹⁴⁻¹⁶ with one finding it the most universally agreed upon consideration.¹⁵ Privacy concerns are likely related to the relatively low levels of sexual orientation disclosure,¹⁷ which is also independently associated with lower likelihood of HIV testing.^{15,17,18} For individuals who wish to maintain privacy, or to avoid potential disclosure of their sexual identity to clinicians or service providers, home services for HIV prevention may be a good option. One study found 57% of their sample was interested in home HIV testing,¹⁵ and our four-city study found that 66% of Blued app users would order a home HIV test kit from the app if it were offered.

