6.0 MEASURES

A summary table of study measures, and sources for each measure, are provided in the table below. Measurement of tenofovir-diphosphate (TFV-DP) levels will be conducted using liquid chromatography/tandem mass spectrometry methods on DBS samples. TFV-DP level can be translated to an interpretation that indicates mean number of days per week PrEP is ingested over a period of approximately one month. The cutpoint used will be TFV-DP levels considered a surrogate for substantial protection: >700 fmol/punch, a level indicating >4 doses/wk.

Construct	Measure	Data source	Definition	Analysis
PRIMARY OUTCOMES				
Feasibility	Home HIV test orders	Order fulfillment	Proportion of participants sent a home HIV test	Benchmark ≥ 30%
Feasibility	Condom orders	Order fulfillment	Proportion of participants sent 'choice' condom package	Benchmark ≥ 30%
Feasibility	PrEP initiation	Clinical site data	Proportion of participants receiving a PrEP prescription	Benchmark ≥ 20%
Acceptability	Systems Usability Scale ^{126, 127}	Survey	10-item scale, good score is >71	Benchmark: Good score (≥ 71 out of 100)
Acceptability	Ratings for intervention components ⁷²	Survey	Likert acceptability rating for each intervention component (e.g. home HIV test)	Benchmark: Acceptable ratings (≥ 3 out of 5)
PRELIMINARY EFFICACY ASSESSMENT				
HIV testing	HIV testing ^{44,128}	Survey	Change in median number HIV tests	GEE model
Condom use	Condom use ^{44,128}	Survey	Change in proportion of participants reporting always using condoms for anal sex	GEE model
PrEP Use	PrEP use ¹²³⁻¹²⁵	Laboratory data	Number participants with protective levels of TDF-DP	Descriptive report
THEORETICAL ASSESSMENT				
Prevention cascade	PrEP cascade levels ¹²⁹	Survey and clinical site data	PrEP awareness, willingness, prescription, persistence in care, and medication adherence	Descriptive and logistic regression
Theoretical assessment	Unified Theory of Acceptance and Use of Technology (UTAUT2) ¹²¹	Survey	Validated items for performance expectancy, effort expectancy, social influence, hedonic motivation, and habit.	Descriptive and GEE model to estimate SEM parameters
PROCESS OUTCOMES				
Process	New HIV testers	Survey	Proportion changing from never to ever HIV test	Descriptive report
Process	New condom users	Survey	Proportion changing from none to some condom use	Descriptive report
Process	Visits to local health clinics	Survey	Proportion receiving HIV services at health departments	Descriptive report

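### Summarised as a median over quarterly windows, the HIV-testing change would most likely read 0 versus 0, and the plan does not state the counting window

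*Combined protocol and SAP*

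**What the plan says.** The measures table in section 6.0 defines the HIV-testing row of the preliminary efficacy block as "Change in median number HIV tests", with survey data as the source and a GEE model as the analysis. Section 10.3 repeats the summary, describing the intervention "compared to the baseline period, for the median number of HIV tests". The GEE that section 10.3 then specifies has a binary outcome, tested or not tested: "Time will be considered as a fixed effect to compare proportion tested across intervals".

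The Schema (Study Design) sets the periods: "a three-month baseline standard of care (SOC) period with measurement at 0 and 3 months will be followed by a 12-month intervention period". Intervention surveys are at 6, 9, 12 and 15 months.

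The Introduction gives two background testing levels. One is the team's own: "our four-city survey found 52% annual testing prevalence". The other comes from a systematic review: "annual period prevalence of HIV testing of 38% among MSM in the most recent reporting period".

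Neither section states the recall window for the number of tests, or whether intervention counts are taken per quarter or summed over 12 months.

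**The concern.** A median of a count is 0 whenever fewer than half of the men have a count of at least one. If about half of men or fewer test in a whole year, far fewer are likely to test in a 3-month window. A quarterly median would then sit on its floor before and after the intervention. If the windows differ in length, the median can move for that reason alone.

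This row is the only measure of testing frequency in the preliminary efficacy block. The Schema says the pilot should supply key parameters for a definitive study, and section 10.2 says these assessments will inform future trial design. A result of 0 versus 0, or a change produced by window length, gives neither a baseline rate nor an effect size. The mismatch between the tabulated median and the modelled proportion also leaves the listed endpoint without an analysis of its own.

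**Working it through.** **The plan's own figure.** The plan gives no figure for the median. Its only precision statement is in section 10.2: half-widths of 4, 5 and 5 points at 20%, 30% and 50%. With 1.96 × √(p(1−p)/400) these come to 3.92, 4.49 and 4.90 points, which agrees if 4.49 is rounded up.

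**Inputs.** Annual testing a = 52% or 38% (Introduction); n = 400; baseline 3 months, intervention 12 months (Schema). Assumption: constant-rate (Poisson) testing, so P(at least one test in m months) = 1 − (1 − a)^(m/12). Uneven testing is examined below.

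**Equal 3-month windows**
- At 52%: rate = −ln(0.48) = 0.734 per year; quarterly share = 1 − 0.48^(1/4) = 16.8%; median 0.
- At 38%: rate = −ln(0.62) = 0.478 per year; quarterly share = 1 − 0.62^(1/4) = 11.3%; median 0.
- Doubling the 52% rate gives 1 − 0.48^(2/4) = 30.7%. Tripling it gives 1 − 0.48^(3/4) = 42.3%. The median is still 0 in both cases.
- Half of men test in a quarter when the rate is ln 2 = 0.693 per quarter, or 2.77 per year. That is 2.77/0.734 = 3.8 times the 52% rate and 2.77/0.478 = 5.8 times the 38% rate. It corresponds to annual testing of 1 − 0.5^4 = 94%.
- Home-test benchmark (30%): even if all 30% were additional testers in one quarter, 16.8 + 30 = 46.8%, still below half.

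**Without the constant-rate assumption.** The share testing in a quarter cannot exceed the share testing in the year. At 38% the baseline median must be 0. At 52% it is 0 unless about 50/52 = 96% of annual testers test in that same quarter. With gamma-Poisson variation (dispersion k from 10 to 0.25, annual share held at 52%) the quarterly share is 17% to 35%, so the median is 0. At k = 0.25 the mean is 0.25 × (0.48^(−4) − 1) = 4.46 per year, or 1.115 per quarter. Half of men testing needs 0.25 × (2^4 − 1) = 3.75 per quarter, a 3.4-fold rise.

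**PrEP users' own tests.** Sections 5.4.4 and 5.4.6 have PrEP users HIV-tested every three months. If 20% are on PrEP (the section 6.0 benchmark) and report those tests, the rest need (0.50 − 0.20)/0.80 = 37.5% per quarter. That is −ln(0.625)/(0.734/4) = 0.470/0.1835 = 2.6-fold.

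**What a proportion would show instead.** Going from 16.8% to 25% per quarter, treated as two independent groups of 400, has power of about 82%; to 30%, about 99%. In both cases the chance of a sample median of at least 1 is 0.0000 to four decimals. That chance is 2% at a true quarterly share of 45% and 97% at 55%.

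**Unequal windows, no effect**
- At 52%: the 3-month median is 0, and P(Binomial(400, 0.52) ≥ 201) = 0.77 that the 12-month sample median is at least 1 (0.75 at n = 320). In 20,000 simulated null trials the 12-month median exceeded the 3-month median in 80%, counting sample medians of 0.5.
- At 38%: the same probability is about 4 × 10⁻⁷.
- The proportion tested would also be inflated: 16.8% versus 52%.

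**The case against.** The strongest reply is that the documents do not fix the window. The survey is not included, and the measures table cites references 44 and 128 for this item while the reference list ends at 26, so the recall wording may sit elsewhere. A 12-month look-back at month 0 and again at month 15 would give equal windows, and the second would cover exactly months 3 to 15. Under constant-rate testing that median can move: from 1 to 2 at about 1.68 tests per year from 52% (1.68/0.734 = 2.3-fold), or from 0 to 1 at 0.693 per year from 38% (0.693/0.478 = 1.45-fold). A reader might infer that no reading of the plan gives a valid change; this one does.

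Second, section 10.3 only describes the median. The modelled outcome is tested versus not tested, which does not have the median's floor. Third, the primary analysis is feasibility and acceptability, and section 10.2 says the pilot is not powered for change from baseline. Fourth, the 52% comes from a general app survey, while enrolled men must be behaviourally eligible for PrEP and may test more.

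The first two points stand and make the concern conditional and limited. The third does not answer it, because the issue is the choice of summary and not the sample size. The fourth changes little: under constant-rate testing the quarterly median stays at 0 up to about 94% annual testing. The binary GEE also needs equal windows, and it does not measure frequency.

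**Conclusion.** The point holds in conditional form. On 3-month windows, which the quarterly surveys make the natural reading, the median is 0 at either background figure. It cannot register an effect that leaves quarterly testing below about 50%. From 52% that means a 3.8-fold rate rise under constant-rate testing, about 3.4-fold with strongly uneven testing, and about 2.6-fold if 20% of men report quarterly PrEP tests. On unequal 3- and 12-month windows, a rise from 0 to 1 with no effect has probability about 0.77 at 52% and n = 400, and is essentially absent at 38%.

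Three stronger readings are not supported:
- That the median can never detect an effect. It responds once more than half of men test in a quarter.
- That a false rise is certain. It depends on an unstated window and on 52% lying just above one half.
- That all inference on HIV testing fails. The binary GEE on equal windows gives a usable estimate.

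What the documents do show is an unstated window, a tabulated endpoint that differs from the modelled one, and a summary poorly suited to the planned survey interval. The primary outcomes are not affected.

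**What to change.** In sections 6.0 and 10.3:

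1. State one 3-month recall window for every survey that enters the comparison, including month 0, and apply it to both the count and the binary outcome. Do not set a 12-month count or proportion against a 3-month one.
2. Make the section 6.0 definition match the modelled outcome: the proportion tested per 3-month interval.
3. Report testing frequency as mean tests per participant per 3 months, with a rate ratio against baseline from a log-link count GEE with robust standard errors. Keep the median only as a descriptive line.

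The cost is a wording change in two sections and one extra model on survey data already planned; the recall wording of the survey item should be checked against it. The mean is sensitive to a few very frequent testers. Robust errors allow for the extra variance, and a result with high counts capped can be shown alongside. If the count model is not wanted, items 1 and 2 alone remove the mismatch and the window problem, but leave frequency unmeasured beyond the descriptive median.

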3.2 Sample Size

Over the entire study period, 400 participants will be enrolled in the prospective pilot study intervention. All participants will be followed longitudinally for 15 months.

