5.3.2 Additional Blued+ Components

After the 3-month period, additional app components will be unlock in the health portal for each participant. These intervention components include:

Educational materials focused on PrEP as well as other sexual health topics. Topics of education may include an overview of PrEP and PrEP medication, the effectiveness of PrEP, PrEP payment, side effects, stigma, and where to access PrEP, among other topics related to prevention of HIV and STIs.

Additionally, participants will receive theory-based sexual health and prevention messages delivered via the Blued+. These messages will be developed with the goal of creating a comprehensive messaging package to improve participants' self-reported sexual health and prevention behaviors, beliefs, and attitudes. Participants will also receive a screener quiz that allows them to assess whether PrEP is right for them and encourage them and link to PrEP care. Those participants who do choose to initiate PrEP will receive the FTC/TDF, associated laboratory testing, and clinical care free of charge. Participants will be encouraged to schedule a visit with a study provider in each intervention city in-person or online, and will access PrEP free of charge through these study clinics.

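### Section 10.3 defines the primary GEE comparisons on a schedule the study does not have, so their months and labels cannot both be followed and no reading uses month 3 as the pre-intervention reference

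*Combined protocol and SAP*

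**What the plan says.** The Schema (Study Design) sets out "a three-month baseline standard of care (SOC) period with measurement at 0 and 3 months will be followed by a 12-month intervention period". For the intervention phase it then gives the survey months: "with the measurement at 6, 9, 12, and 15 months". Section 3.0 counts "a total of six surveys for each participant comprising enrollment/baseline (two surveys) and pilot intervention (four surveys", and section 11.5 pays for six surveys at those same months. Section 3.2 fixes the end of follow-up: "All participants will be followed longitudinally for 15 months". The intervention starts at month 3, according to the Schema and section 5.3.2: "After the 3-month period, additional app components will be unlock in the health portal for each participant".

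Section 10.3 gives the aim as follows: "Preliminary efficacy assessments will describe differences in outcomes for the intervention, compared to the baseline period". The model is then specified: "The GEE model will contain the seven time periods with primary comparisons of 0-month (first baseline) measurement to 6-month (end wash-out baseline period measurement", continuing "and to 12-month (end first intervention period) measurement". Time enters as a fixed effect, and the condom outcome is to be modelled in a similar way. Section 10.4 adds the UTAUT2 constructs to these same models. In the same section 10.3, the PrEP cascade analysis runs from month 0 to month 15, which fits the six-survey schedule.

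Section 10.2 says that the additional analyses measure change between the baseline and intervention phases, draw on the interrupted time series design, and inform the design of a later trial.

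**The concern.** The sentence that defines the primary comparisons uses a period count, a wash-out phase and a numbered intervention period that appear nowhere else in the text. Month 6 is called the end of baseline, yet by then participants have had the intervention for three months. Month 12 is called the end of a first intervention period, yet there is only one, and it ends at month 15.

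An analyst therefore has to choose between the month numbers and the labels, and the choice changes which contrasts are reported as primary. Nothing stops that choice being made after the data are seen. The wording also carries over to the condom model and the UTAUT2 models. The results are meant to inform the design of the later trial, so it matters whether a reported change includes SOC time, or whether early intervention change is reported as baseline change.

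**Working it through.** **Period count.** Section 10.3 states seven. The schedule is months 0, 3, 6, 9, 12 and 15: six measurements and five intervals. Neither count gives seven. A seventh quarterly measurement would fall at 6 × 3 = month 18, after follow-up ends.

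**Which contrasts result.** Months 0 and 3 are SOC; months 6 to 15 are intervention. This assumes that each survey reflects the quarter before it, since the documents give no look-back window.

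| Reading of 10.3 | First comparison | Second comparison |
|---|---|---|
| Month numbers followed | 0 to 6: SOC versus 3 months of intervention | 0 to 12: SOC versus 9 months of intervention |
| Labels moved to the real schedule | 0 to 3: no intervention time | 0 to 15: SOC versus 12 months of intervention |
| Stated months keep their labels | 0 to 6, reported as baseline change | 0 to 12, called the end of a period that ends at 15 |

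On the month-number reading, months 3 and 15 appear in no named GEE contrast. On no reading is month 3 the reference for a baseline-versus-intervention contrast.

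**Effect of the reference month.** Assume a linear background drift of b points per quarter and no intervention effect. Each contrast then carries b × (number of quarters spanned):

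- 0 to 6: 2b; 3 to 6: b; difference b.
- 0 to 12: 4b; 3 to 12: 3b; difference b.
- 0 to 15: 5b; 3 to 15: 4b; difference b.

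At any matched month, the month-0 reference adds exactly one quarter of drift. For illustration, take an assumed 10-point step effect and b = 2: 0-to-6 gives 10 + 4 = 14, 3-to-6 gives 10 + 2 = 12, and 0-to-3 gives 2, which is drift alone.

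**Scale against precision.** The 95% half-width of a two-point contrast under exchangeable correlation is 1.96 × √(p(1−p) × (1−ρ) × 2 / n). Assumed inputs are p = 0.5, n = 400 with full retention, and ρ from 0.3 to 0.7.

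- ρ = 0.3: 1.96 × √(0.25 × 0.7 × 2 / 400) = 5.8 points.
- ρ = 0.7: 1.96 × √(0.25 × 0.3 × 2 / 400) = 3.8 points.

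At an assumed 80% retention (n = 320) these become 6.5 and 4.2 points. The four-city survey in section 1.0 gives some support for p on the condom outcome: 1 − 1584/3457 = 0.542, which leaves 5.8 and 3.8 unchanged. For an assumed b of 1 to 3 points, the ratio of b to the half-width runs from 1/5.8 = 0.17 to 3/3.8 = 0.79.

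**The case against.** A reader might infer that the two named comparisons fail to measure baseline-to-intervention change at all. The documents do not support that. By month number, month 0 is a baseline measurement and months 6 and 12 are intervention measurements, so both comparisons match the stated aim. With the labels moved to the real schedule, 0-to-15 matches it too. Including SOC-period change makes a contrast less clean; it does not make it a different kind of contrast.

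A reader might also infer that the label error would cancel a real effect. If an effect is present by month 6 and sustained, 0-to-12 minus 0-to-6 is zero without drift. But 10.3 does not write that subtraction, so the plan cannot be charged with it. It is equally tempting to conclude that the section was carried over from an 18-month design. That would explain the count, but the documents do not show it.

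Three further points have weight. Time is a fixed effect covering all measurements, so month-3 contrasts can be estimated from the planned model; what is missing is a statement of which contrasts are primary. Month 3 as the reference is partly a preference: 3-to-15 carries 4b of drift, the same as 0-to-12, and neither adjusts for trend. And the values of b, ρ and retention are assumptions.

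None of this removes the contradiction. The period count is wrong on any reading, and nothing elsewhere in the text says whether the months or the labels govern.

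**Conclusion.** The point holds as an error in specification and should be fixed before analysis. The count and labels in 10.3 contradict the study's own schedule, the primary GEE contrasts are ambiguous, and the last SOC measurement is not used as the reference for the intervention.

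The numerical consequence is modest and of unknown size. At a matched month it is one quarter of drift, in whichever direction the drift runs. The ratio to the half-width shown above is illustrative and is not evidence of material bias. Changing the reference month does not remove the remaining pre/post drift.

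The analysis is a preliminary-efficacy assessment in a pilot that section 10.2 describes as unpowered. The feasibility and acceptability benchmarks in 10.1 do not use this model and are unaffected.

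**What to change.** Rewrite 10.3 so that the model contains six measurements (months 0, 3, 6, 9, 12 and 15). Delete the count of seven, the wash-out label and the reference to a first intervention period. Name each primary contrast by month and phase before analysis.

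Recommended option:

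- Primary: month 6 (first intervention measurement) and month 15 (end of intervention), each versus month 3 (end of SOC).
- Report the 0-to-3-month change separately as the SOC-period change.
- Describe all contrasts as pre/post changes without trend adjustment.

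If the team prefers month 0 as the reference, 10.3 should say that these contrasts include SOC-period change and should add the month-3 contrasts. The survey look-back windows should be stated either way, since the reading of the 0-to-3-month change depends on them.

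The cost is wording only. All six surveys are already planned, and two primary comparisons are kept. Under exchangeable correlation and equal retention, a two-point contrast with month 3 has the same half-width as one with month 0, so no precision is lost.
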